8.5.6. Safety Monitoring for Potential Hypersensitivity Reactions

Patients will be instructed to promptly report any signs or symptoms of potential hypersensitivity reactions that include the acute onset of the following: urticarial rash, pruritus, flushing, angioedema dyspnea, and/or acute onset hypotension, that may arise during the study. The Investigator should closely evaluate all potential causes, including concomitant illnesses.

Patients who experience symptoms of a potential hypersensitivity reaction should be tested within 15 minutes to 3 hours after onset of symptoms, or as soon as possible thereafter for:

- Tryptase
- High-sensitivity C-reactive protein (hsCRP)
- Erythrocyte sedimentation rate (ESR)
- Complement factors (C3, C4, C5a, and Bb)
- Immunoglobulin E (IgE)
- CBC with differential
- Serum chemistry
- Urinalysis
- UPCR
- Anti-drug antibody (ADA)
- Antinuclear antibody (ANA)
- Antineutrophilic cytoplasmic antibody (ANCA)

If a hypersensitivity reaction is established, Study Drug discontinuation should be recommended. The patient's symptoms should be managed per standard of care.

8.5.7. Safety Monitoring for LDL-C Elevations

Beginning at Week 27, laboratory alerts will be in place to notify the Investigator if a patient has an LDL-C > 130 mg/dL (> 100 mg/dL for patients with T2DM or CAD with Baseline LDL-C > 100 mg/dL) on 2 consecutive visits. If this occurs, LDL-C values for this patient will be unblinded for the remainder of the study and the Investigator will be encouraged to initiate/adjust treatment to lower LDL-C according to country-specific guidelines (e.g., initiate statin therapy or increase the statin dose for patients who are already on treatment).

8.6. Stopping Rules

Monitoring rules are described above in Section 8.5.

For the purposes of stopping rules, Baseline is defined as the average of the Day 1 pre-dose assessment and the last measurement prior to Day 1.

8.6.1. Stopping Rules for Liver Chemistry Elevations

All cases of confirmed laboratory results meeting any of the following criteria, but having an alternative etiology such as congestive heart failure, introduction of a new drug, some identified biliary tract issues etc., must be reviewed by local hepatologist, the DSMB hepatologist, and the decision to restart the Study Drug must be made upon reaching a general agreement between consulting hepatologist, the DSMB hepatologist, and the Sponsor Medical Monitor that the alternative etiology is well supported as the likely cause, and when ALT and AST levels become

\leq 3 × ULN. Until this evaluation is completed and a decision agreed upon, the treatment with the Study Drug will remain interrupted.

In the event of confirmed laboratory results meeting any of the following criteria, **and the event is without an alternative explanation as discussed with the Medical Monitor**, dosing of a patient with Study Drug (ISIS 678354 or placebo) will be stopped permanently; values that are not confirmed due to failure to retest or missing lab values will be presumed confirmed:

- 1. ALT or $AST > 8 \times ULN$, which is confirmed
- 2. ALT or AST > 5 × ULN, which is confirmed and persists for \ge 2 weeks
- 3. ALT or AST > $3 \times$ ULN (or the greater of $2 \times$ baseline value or $3 \times$ ULN if the baseline value was > ULN), which is confirmed **and** total bilirubin > $2 \times$ ULN or INR > 1.5
- 4. ALT or AST > 3 × ULN (or the greater of 2 × baseline value or 3 × ULN if the baseline value was > ULN), which is confirmed, **and** the new appearance (i.e., onset coincides with the changes in hepatic enzymes) of fatigue, nausea, vomiting, right upper quadrant pain or tenderness, fever, rash, and/or concomitant eosinophilia (> ULN)

8.6.2. Stopping Rules for Renal Function Test Results

In the event that the any of the renal monitoring rules summarized in Section 8.5.2 are met, treatment with Study Drug should immediately be interrupted and the abnormal result should be confirmed as soon as possible, but no later than 7 days after the initial event. In addition, upon consultation with the Medical Monitor, the site will obtain any additional lab assessments necessary to determine any alternative etiologies that may account for the abnormal result. If results from additional testing confirm the initial abnormal lab result(s) described in Section 8.5.2, and additional evaluations regarding etiology accounting for these abnormalities are completed, future treatment of the patient will be determined per the guidelines below:

- An alternative etiology is identified that may account for abnormal results
 - Patient will have treatment with Study Drug interrupted until either:
 - Lab values have returned to baseline, and/or
 - Alternative etiology has resolved/recovered, AND
 - Study Medical Monitor has approved Study Drug treatment to resume
- An alternative etiology has not been identified that may account for abnormal results:
 - o Patient will be permanently withdrawn from Study Drug treatment

The follow-up schedule and frequency of renal function monitoring after the initial event will be determined by the Medical Monitor in consultation with the Investigator. The Investigator should consider consulting a local nephrologist for any change of renal function that presents a concern. If a renal biopsy is performed, a sample specimen should be made available for examination by an independent renal pathologist who has been engaged by the Sponsor to review such specimens.

8.6.3. Stopping Rule for Platelet Count Results

Actions to be taken in the event of a low PLT count are summarized in Table 2 above.

8.6.4. Stopping Rule for Bleeding Events

In the event of Major Bleeding or Clinically Relevant Non-major Bleeding (see definitions in Section 8.5.4 as assessed by the Investigator, dosing of a patient with Study Drug (ISIS 678354 or placebo) may be stopped permanently. The follow-up schedule for any events meeting this stopping criterion will be determined, including the suitability of the patient for resumption of dosing by the Investigator in consultation with the Medical Monitor (or designee).

8.7. Adjustment of Dose and/or Treatment Schedule

Dose adjustments for platelet count reduction must be made in accordance with Table 2 (above).

Other adjustments, including dose interruptions, and/or decreasing the dose will be allowed for safety or tolerability after consultation with the Sponsor Medical Monitor.

Dose adjustments should not occur unless absolutely necessary prior to the primary analysis time point (Month 6).

8.8. Discontinuation of Study Drug

A patient must permanently discontinue Study Drug treatment for any of the following:

- The patient becomes pregnant. Report the pregnancy according to instructions in Section 9.5.4
- The patient withdraws consent
- The patient experiences an AE that necessitates permanent discontinuation of Study Drug
- The patient develops laboratory test abnormalities that meet any of the stopping rules listed in Section 8.6.1 to Section 8.6.3
- The patient experiences an AE that necessitates unblinding of the Investigator or Sponsor to the patient's treatment assignment

The reason for discontinuation of Study Drug must be recorded in the eCRF and source documentation.

8.8.1. Follow-up Visits for Early Termination from Treatment Period or Post-Treatment Follow-up Period

Any patient who discontinues early from the Treatment Period should be strongly encouraged to attend applicable landmark visits at Weeks 23, 25, 27 and Weeks 51 and 53 (calculated based on the time elapsed since Day 1) to collect fasting lipid panels and conduct safety assessments in accordance with Appendix A. Any patient who discontinues early from the Post-Treatment Follow-up Period should be strongly encouraged to complete follow-up study visits, procedures and observations in accordance with Appendix A.

Any patient who discontinues early from the Treatment Period or from Post-Treatment Follow-up Period should be followed as per the platelet monitoring rules shown in Table 2, Section 8.6.3 for the first 6 weeks Post-End of Treatment Period and then at 8 and 13 weeks Post-End of Treatment Period (as per visit schedule).

If a patient discontinues early from the Treatment Period and declines or is unable to participate in the above, an ET visit (Week 53 visit assessments) should be performed at the time of withdrawal, and ideally within 2 weeks from the last dose of Study Drug, and patients should start the 13-week Post-Treatment Follow-up Period to collect the study assessments in accordance with the Schedule of Procedures in Appendix A.

If the patient discontinues early from the Post-Treatment Follow-up Period and declines or is unable to participate in the above, a final visit (assessments from Week 13 of the Post-Treatment Follow-up Period) should be performed at the time of withdrawal.

8.9. Withdrawal of Patients from the Study Procedures

Patients must be withdrawn from study procedures for any of the following:

- Withdrawal of consent
- The patient is unwilling or unable to comply with the protocol
- The patient meets any of the Exclusion Criteria (see Section 5.2) after enrolling in the study that in the opinion of the Investigator represents a safety risk to the patient

Other reasons for withdrawal of patients from study procedures might include:

- At the discretion of the Investigator for medical reasons
- At the discretion of the Investigator or Sponsor for noncompliance
- Significant protocol deviation

All efforts will be made to complete and report the observations as thoroughly as possible up to the date of withdrawal. All information, including the reason for withdrawal from study, must be recorded in the eCRF.

Any patient who withdraws consent to participate in the study will be removed from further treatment and study observation immediately upon the date of request. These patients should be encouraged to complete the early termination study procedures and observations at the time of withdrawal Appendix A.

For patients withdrawn for reasons other than withdrawal of consent every effort should be made to complete the early termination of study procedures and observations at the time of withdrawal (see Appendix A) and ideally within 2 weeks from the last dose of Study Drug.

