10.6.3. Efficacy Analysis

10.6.3.1. Analysis of Primary Endpoint

The primary analysis of the primary endpoint is to compare the percent change from Baseline to the primary analysis time point in fasting TG between each ISIS 678354 treatment group vs. pooled placebo using an ANCOVA model in the FAS. The ANCOVA model will include the effects of treatment (ISIS 678354 80 mg, ISIS 678354 50 mg, or Placebo), 2 randomization stratification factors (history of pancreatitis and previous treatment with volanesorsen), and log-transformed baseline TG. To account for potential heterogeneity in variance, the 95% CI of the treatment differences will be calculated using the robust variance estimator based on the Bell and McCaffrey method (Imbens and Kolesár 2016). If patients have intercurrent event(s) before Week 23, e.g., treatment discontinuation, use of additional medication, changes in background or concomitant treatments, the Treatment Policy strategy will be implemented, the patients' assessments post intercurrent events will continue to be collected and utilized in the primary analysis. Patients with a missing TG value after discontinuation will have TG value multiply imputed at Primary analysis time point based on the known assessments from the retrieved dropouts (i.e., patients who discontinue before Week 23 but still have TG assessments at

Week 23, 25 or 27), if there is a sufficient number of retrieved dropouts. The imputation model will include the following variables: TG values at baseline and post-baseline visits and the 2 randomization stratification factors. The multiple imputation will be stratified by treatment group. If there is not a sufficient number of retrieved dropouts, missing TG value at the primary time point will be imputed using a "wash-out" (Jump to Reference, J2R) multiple imputation approach. With the approach, patients treated with ISIS 678354 who discontinue study will have missing post-discontinuation TG values multiply imputed based on the fasting TG at Baseline, 2 randomization stratification factors, and the imputation model for the placebo group. Patients in the placebo group who discontinue the study will have missing post-discontinuation TG values at Baseline and post-baseline visits from the placebo group.

It is anticipated that the rate of missing data is low.

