4.9.2. Primary Efficacy Variable

The primary efficacy analysis will take place after the last patient has completed the Week 53/ET visit and the database has been locked, and will be based on the percent change from Baseline in fasting TG at primary analysis time point.

The primary endpoint is the percentage change in fasting TG from Baseline to the primary analysis time point. The primary analysis of the primary endpoint is to compare the percent change from Baseline to the primary analysis time point in fasting TG between each ISIS 678354 treatment group (ISIS 678354 80 mg, ISIS 678354 50 mg) vs. pooled placebo using an ANCOVA model in the FAS. The ANCOVA model will use precent change from Baseline to the primary analysis time point in fasting TG as dependent variable, the two randomization stratification factors, prior history of pancreatitis within 10 years prior to Screening (yes vs. no), previous treatment with Volanesorsen (yes vs. no) and treatment group (ISIS 678354 80 mg, ISIS 678354 50 mg) as the fixed effects and nature log-transformed baseline fasting TG as a covariate. To account for potential heterogeneity in variance, the 95% CIs will be calculated using the robust variance estimator based on the Bell and McCaffrey method (Imbens & Kolesár 2016).

If patients have intercurrent event(s) before Week 23, e.g., treatment discontinuation, use of additional medication, changes in background or concomitant treatments, the Treatment Policy strategy will be implemented, the patients' assessments post intercurrent events will continue to be collected. All assessments including those post the intercurrent events will be utilized in the analysis.

Patients with missing TG value at the baseline and/or primary analysis time point will have fasting TG value multiply imputed using the multiple imputation methods described in Section 4.9.1.2 in the SAP. The are provided in the table below:

Treatments	ISIS 678354 80 mg Pooled placebo
Participant Population	Patients with FCS as defined by protocol eligibility criteria
Variable	Percent change from Baseline to primary analysis time point (average of Weeks 23, 25 and 27) in fasting TG
Intercurrent events (ICEs) and strategies	Discontinuation of study treatment prior to Week 23 Treatment policy strategy Disallowed concomitant therapy/procedure prior to Week 23 Treatment policy strategy
Population-level summary	Difference in means between ISIS 678354 80 mg and pooled placebo in the FAS

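### Protocol 8.9 withdraws some patients from study procedures without pointing to the landmark follow-up in 8.8.1, at odds with the treatment-policy estimand

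*Combined protocol and SAP*

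**What the plan says.** Protocol 8.9 opens its mandatory list with "Patients must be withdrawn from study procedures for any of the following". Besides withdrawal of consent, the list has two grounds:

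- "The patient is unwilling or unable to comply with the protocol";
- an exclusion criterion that comes to apply after enrolment, if the Investigator judges it a safety risk.

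A second, optional list covers medical reasons, significant deviation, and withdrawal "At the discretion of the Investigator or Sponsor for noncompliance". Noncompliance is therefore both a mandatory and a discretionary ground.

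For patients who leave for reasons other than consent, 8.9 says that "every effort should be made to complete the early termination of study procedures and observations at the time of withdrawal", ideally within two weeks of the last dose. It does not refer to 8.8.1.

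Protocol 8.8.1 says that any patient who stops the Treatment Period early "should be strongly encouraged to attend applicable landmark visits at Weeks 23, 25, 27 and Weeks 51 and 53", for fasting lipids and safety assessments.

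On analysis, protocol 10.6.3.1 applies a treatment-policy strategy under which "the patients' assessments post intercurrent events will continue to be collected and utilized in the primary analysis". SAP 4.9.2 agrees: "All assessments including those post the intercurrent events will be utilized in the analysis". SAP 4.9.3.5 treats adjudicated pancreatitis events after intercurrent events in the same way.

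**The concern.** A treatment-policy estimand needs patients to be observed after they stop or change treatment. Section 8.9, followed literally, ends observation for some patients who would still attend. Three things are at stake.

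- **Primary endpoint.** A patient withdrawn well before Week 23 has no Week 23, 25 or 27 triglyceride value. A later withdrawal affects Month 12 and pancreatitis follow-up only.
- **Imputation.** The first-choice method borrows from retrieved dropouts, meaning patients who stop before Week 23 but still have a value at Week 23, 25 or 27. Each patient withdrawn under 8.9 is one fewer. The plan gives no number for what counts as sufficient, so losing a few could trigger the jump-to-reference (J2R) fallback.
- **Pancreatitis.** Events after withdrawal are not captured. The observation-time offset corrects for shorter exposure, but not for withdrawal that is related to risk.

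These patients are selected on compliance or perceived safety, so their missing values could be informative.

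**Working it through.** **1. The sections side by side**

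| Situation | One instruction | Other instruction |
|---|---|---|
| Noncompliant patient who is willing to attend visits | 8.9: must leave procedures (first list), or may leave (second list) | 8.8.1: encourage the landmark visits |
| Disallowed therapy before Week 23, such as systemic corticosteroids (exclusion criterion 12a) | 8.9: must leave procedures if judged a safety risk | SAP 4.9.2: treatment policy, later data used |
| Pancreatitis after an intercurrent event | 8.9: only early-termination procedures requested | SAP 4.9.3.5: events still collected |

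**2. The plan's own sample size**

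Inputs (protocol 10.2, SAP 4.12): difference 60 points, SD 46, two-sided alpha 0.05, 14 per group, 90% power.

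Noncentrality = 60 / (46 × √(2/14)) = 3.45 on 26 df, so power is 91.3%. With 13 per group it is 89.1%. Fourteen is the smallest group size that reaches 90%, and the stated figure reproduces.

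**3. Planned enrolment**

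About 60 patients, split 1:1 by cohort and then 2:1, give about 20 on each dose and 20 on pooled placebo.

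Noncentrality = 60 / (46 × √(2/20)) = 60 / 14.55 = 4.12 on 38 df, so power is 98.0%.

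**4. Shift per patient if J2R is used**

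Assume no change on placebo, as in the sample-size section. A fraction f of an active arm imputed as placebo gives a difference of 60 × (1 − f).

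- One of 20: 60/20 = 3 points, leaving 57.
- Two of 20: 54.
- Four of 20: 48.

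**5. Power if J2R is used**

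Active-arm variance = 46² + f(1 − f) × 60². This is averaged with the placebo variance of 2116.

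| Imputed per active arm | Difference | Averaged variance | SE | Noncentrality | Power |
|---|---|---|---|---|---|
| 0 | 60 | 2116 | 14.55 | 4.12 | 98.0% |
| 2 | 54 | (2440 + 2116)/2 = 2278 | 15.09 | 3.58 | 93.7% |
| 4 | 48 | (2692 + 2116)/2 = 2404 | 15.50 | 3.10 | 85.5% |

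Simulating J2R with Rubin's rules, without covariates, gives about 98%, 94–95% and 84–89%. The lower ends apply when as many placebo values are missing too.

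**6. How much of the shift is bias**

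If a withdrawn patient would have kept a reduction of r points off drug, J2R biases the estimate by f × r.

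| | r = 20 | r = 40 | r = 60 |
|---|---|---|---|
| f = 10% (2 of 20) | 2 | 4 | 6 |
| f = 20% (4 of 20) | 4 | 8 | 12 |

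If triglycerides rebound fully (r = 0), the observed data would themselves average about 54 or 48, and J2R adds no bias.

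**The case against.** The strongest reply is that few patients fall into the gap.

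- **Laboratory findings.** A reader might infer that 8.9 removes patients with low platelets, raised transaminases or renal changes. The documents do not support this as a general mechanism. Protocol 8.5 and 8.6 give these results their own rules, which act on Study Drug. Protocol 8.5 sends patients who meet the liver, renal or platelet stopping criteria to follow-up under 8.8, and 8.8.1 then applies. The laboratory exclusion criteria are framed as screening results. Protocol 4.1 counts a patient as enrolled at consent, so 8.9 also covers people who are never randomized.
- **Reach of 8.8.1.** It covers any patient who stops the Treatment Period early and does not exclude those withdrawn under 8.9. Section 8.9 does not expressly forbid later visits outside withdrawal of consent.
- **Cause of the loss.** Where a patient will not or cannot attend, no wording recovers the data.
- **Safeguards.** The plan enrols about 60 against 42 needed (3 × 14), and includes completer, copy-increment-from-reference and tipping-point analyses. J2R is only the fallback.

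The first, third and fourth replies stand, and they shrink the affected group and its effect. The second shows that a compatible reading exists. However, a site told that a patient must leave study procedures cannot be expected to find that reading without a cross-reference, and the double listing of noncompliance remains.

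**Conclusion.** The conflict is real and limited. Section 8.9 as written can end data collection in patients who would still attend, while 8.8.1 and the treatment-policy strategy assume that collection goes on. Data up to withdrawal are kept; what is lost is later follow-up. The number affected cannot be derived from the documents.

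If J2R is used, the shift is about 3 points toward placebo per active patient. Power is about 98% with none imputed, 94–95% with two per active arm and 84–89% with four. This assumes 20 per arm, SD 46, a 60-point effect and no placebo change. With that much slack, alignment with the estimand and possible bias matter more than power.

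Two stronger readings are not supported:

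- **That 8.9 causes the whole power loss.** Part of it comes from stopping drug, and would appear even with complete follow-up.
- **That such withdrawals are more frequent on active drug.** The lay summary reports treatment stopped for side effects in 2 of 22 patients on 80 mg and none in the other groups. That concerns Study Drug, not withdrawal from procedures under 8.9.

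**What to change.** Reconcile protocol 8.9 with 8.8.1 and 10.6.3.1 and with SAP 4.9.2 and 4.9.3.5, by separating discontinuation of Study Drug from the end of data collection.

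- State in 8.9 that patients withdrawn for reasons other than withdrawal of consent remain eligible for, and are encouraged to attend, the 8.8.1 landmark lipid, safety and pancreatitis follow-up, where they are willing and the Investigator considers the assessments safe.
- Add the cross-reference to 8.8.1, and resolve the double listing of noncompliance.

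Decisions on Study Drug, and on safety-based withdrawal from individual procedures, stay with the clinical team. No clinical ground in 8.9 needs to be deleted.

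The cost is protocol wording and a few follow-up visits.

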8.10. Concomitant Therapy and Procedures

The use of concomitant therapies or procedures defined below must be recorded on the patient's eCRF. Adverse events related to administration of these therapies or procedures must also be documented on the appropriate eCRF.

